The low tear interchange rate reported by Polse suggests that if corneal edema is to be prevented with contact lens wear, the material must have high enough oxygen transmissibility to meet the oxygen needs of the cornea. This observation is consistent with the predictions by Fatt and Lin (Fatt I L. D., 1976) and Fatt and Hill (Fatt I H. R., 1970), who have shown that the contribution of tear flow to the oxygen tension at the anterior cornea for most low Dk/t hydrogel lenses would be as low as 4 mmHg. Many currently used hydrogel contact lenses can only supply adequate oxygen to the cornea directly by diffusion if the lens thickness is less than 0.10 mm (Decker M, 1978).

Study Objective

- I. Evaluate corneal oxygen uptake of a new translating contact lens design with comparison to published data and commercially available designs.
- II. Evaluate subjectively reported comfort of a new translating contact lens design with comparison to commercially available designs.

[figure not shown]
Hypothesis

We hypothesize that the Apioc lens design will provide greater tear exchange behind this novel soft contact lens than a standard soft contact lens. Its patented design suspends the lens from the upper eyelid thus allowing a looser fit and greater movement of the contact lens over the ocular surface than standard thickness soft contact lenses. These design aspects should lead to an increase in tear exchange behind the contact lens. Because tear exchange behind a soft contact lens is very difficult to measure on the human eye, and there is no tear exchange rate benchmark that is correlated with direct clinical benefits, the impact of the Apioc contact lens design will be assessed indirectly by measuring corneal oxygen uptake, as the cornea receives its oxygenation through the tears. Thus, our experimental hypothesis is that the cornea wearing the Apioc contact lens will have an oxygen uptake rate of ≥ 10 mm Hg.

Apioc is manufactured in Definitive 74 contact lens material (Dk/t = 44) (Benjamin, 2018). If the Apioc contact lens and standard contact lens have center thickness of 0.20 mm, then the Dk/t of the lenses is 22 which correlates with 9 percent EOP. If the Apioc lens movement with blinking at a normal blink rate allows greater oxygen delivery by 30 percent to 12 percent EOP, (See illustration by Benjamin below) it will allow normal corneal thickness, (prohibit corneal swelling) in daily wear. This provides a clinical benchmark demonstrating

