In this study, an experienced clinician will apply the oxygen electrode as described above to one eye of up to 10 subjects who are experienced contact lens wearers, eyecare clinicians or clinicians-in-training, and have no active ocular conditions that would preclude short term contact lens wear.

There will be up to five scenarios that will be examined at each visit: cornea with no stimulus to represents the high oxygen condition; immediately after gently closing their eyes for 5 minutes to represent the low oxygen condition; and after contact lens wear. Lens options include Apioc lens design with lenticular, Apioc lens design without lenticular, and commercially available contact lenses. The contact lens conditions will be worn with normal blinking – every four seconds for five minutes prior to oxygen uptake measures. The scenarios will be randomized to minimize bias.

Each of these measurements lasts less than one minute and are repeated at two additional visits.

A rest period of at least ten minutes of normal open eye blinking should be allowed between measurements of the same eye.

The conjunctiva of the subject will be examined prior to probe applications and between probe applications to assess ocular irritation induced by the probe. An increase in two grades on to the Brien Holden Vision Institute Grading Scales (see appendix) will indicate a need to discontinue measurements for the day.

Screening

- I. Statement of Informed Consent
 - A. Prior to enrollment, each subject must read, understand, and sign the informed consent document. It must also be signed by a study team member who is authorized to consent subjects.
 - B. Each subject must be given a signed version of this document.
- II. Eligibility
 - A. All criteria must be met.
 - B. All responses to Inclusion Criteria must be “yes.”
 - C. All responses to Exclusion Criteria must be “no.”

III. Demographics – Age (in years and months)

Baseline Visual and Ocular Assessment

- I. Measure presenting visual acuities: OD, OS
- II. Anterior segment slit lamp examination
 - A. Ocular abnormalities noted
 - B. Eligibility – examiner will determine if subject continues to meet inclusion/exclusion criteria

Oxygen Consumption of the Cornea Measurement

- I. Setup equipment in accordance with the procedure manual.
- II. Instill 1 drop of artificial tears into the eye that will not be measured.
- III. Experimental Conditions
 - A. High oxygen conditions: normal open eye conditions with normal blinking

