 - B. Low oxygen conditions: close both eyes for 5 minutes prior to testing
 - C. Soft contact lens conditions: apply contact lens to test eye and wait at least 5 minutes. Blink to a metronome set at 15 blinks per minute. Remove the contact lens immediately before the probe is applied in step IV below. In one visit, measure up to three different contact lens designs in a randomized order:
 - i. Apioc lens design with lenticular
 - ii. Apioc lens design without lenticular
 - iii. Standard lens design with a thickness equivalent to the mean thickness of the Apioc design with lenticular
 - iv. Commercially available contact lenses
- IV. Collect measurements in accordance with the procedure manual.
 - A. Measurements will be randomized to minimize bias.
 - B. Measurements will be repeated if initial review of data indicates poor quality.
- V. Determine whether the study visit is complete.
 - A. Visually assess conjunctival redness. An increase of two grades in bulbar or limbal redness on the reference grading scales indicates the current study visit is complete.
 - B. Ask the subject to complete the comfort assessment (see Appendix). An answer of “no” to question 2 indicates the current study visit is complete.
 - C. A completion of all measurements listed in the conditions above (A, B, and up to three contact lenses for condition C) indicates the current study visit is complete.
- VI. If another measurement will be collected in the current study visit, a rest period of at least ten minutes of normal open eye blinking will be allowed between measurements of the same eye.

Concluding Visual and Ocular Assessment

- I. Measure visual acuities with presenting correction in place: OD, OS
- II. Anterior segment slit lamp examination
 - A. Ocular abnormalities noted

Corneal Oxygen Uptake Calculation

Calculate the slope over a 100 torr drop in oxygen uptake – from 140 torr to 40 torr.

Data Analysis

The study objective is to compare the corneal oxygen uptake rates of the standard conditions (normal open and closed eyes) and test conditions. Paired t-tests will be performed to determine if this objective is met.

The individual performing data analysis will be masked to minimize bias.

Safety and Adverse Events

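### The plan does not secure the permeability-matched lens comparison on which its tear-exchange hypothesis rests

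*Combined protocol and SAP*

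**What the plan says.** The Hypothesis section proposes that "the Apioc lens design will provide greater tear exchange behind this novel soft contact lens than a standard soft contact lens". Tear exchange is not measured; it is to be inferred from corneal oxygen uptake. The supporting argument sets the two lenses equal on diffusion: "If the Apioc contact lens and standard contact lens have center thickness of 0.20 mm, then the Dk/t of the lenses is 22", which the section equates with 9% EOP. It then supposes that Apioc's movement "allows greater oxygen delivery by 30 percent to 12 percent EOP".

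The lenses to be worn are described in three places, and the descriptions differ.

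- Study Objective, I: "Evaluate corneal oxygen uptake of a new translating contact lens design with comparison to published data and commercially available designs".
- Clinical Study Methods: "Lens options include Apioc lens design with lenticular, Apioc lens design without lenticular, and commercially available contact lenses". No standard lens appears.
- Oxygen Consumption of the Cornea Measurement, III.C: both Apioc designs, then iii, "Standard lens design with a thickness equivalent to the mean thickness of the Apioc design with lenticular", and iv, "Commercially available contact lenses". Up to three different designs are measured in one visit.

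No product, material, Dk or Dk/t is given for lens iv, and no material for lens iii. Data Analysis plans paired t-tests of the test conditions against the normal open and closed eye. It names no contrast between lenses and no allowance for Dk/t.

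**The concern.** Uptake reflects all the oxygen that reaches the cornea, whether through the lens or around it. The section Tear Flow Under Hydrogel Contact Lenses reports that, under common hydrogel lenses, most of it arrives by diffusion through the material and little by tear pumping. A difference in uptake between two lenses therefore says something about tear exchange only if diffusion through them is the same. The Hypothesis recognises this by giving both lenses one Dk/t.

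The procedures do not carry that condition through. The study could be run exactly as written and end with no comparison between Apioc and a lens of the same permeability. The lens comparison left would then be with a commercial lens of unknown Dk/t. A more permeable commercial lens could hide a real tear-exchange benefit, and a less permeable one could produce an apparent benefit with no extra tear exchange.

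**Working it through.** **Inputs from the protocol.** Hypothesis: material value 44, center thickness 0.20 mm, Dk/t 22, 9% EOP, hypothesised rise to 12% EOP. The notes that close the Hypothesis section: 9.9% EOP for no edema, and a transmissibility benchmark of 24.1 ± 2.7. III.C: four lens types, up to three per visit.

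**1. The plan's own figure.** The text says "Apioc is manufactured in Definitive 74 contact lens material (Dk/t = 44", but the arithmetic uses 44 as Dk. With Dk in units of 10⁻¹¹ and t in cm, Dk/t = 44 × 10⁻¹¹ / 0.020 = 22 × 10⁻⁹. The stated 22 is reproduced. The gain also agrees to rounding: 9 × 1.30 = 11.7, against the stated 12 (12/9 is a rise of 33%).

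**2. How easily Dk/t moves.** In the same units, Dk/t = Dk / (10 × thickness in mm).

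- The same material at 0.10 mm: 44 / 1 = 44, twice the assumed value.
- The benchmark of 24.1 at 0.20 mm needs Dk = 24.1 × 2 = 48.2, which is 9.5% above 44.
- An unspecified commercial lens, on an assumed range that is not in the documents (Dk 20 to 140, thickness 0.07 to 0.20 mm): from 20 / 2 = 10 to 140 / 0.7 = 200.

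**3. The comparator Dk/t that offsets the hypothesised gain.** Assume that EOP is linear in Dk/t near 22 and that 9.9% EOP corresponds to the benchmark value B. Then slope = (9.9 − 9) / (B − 22), and the offsetting Dk/t = 22 + (12 − 9) / slope.

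| B | Slope (EOP points per unit) | Offsetting Dk/t |
|---|---|---|
| 24.1 | 0.9 / 2.1 = 0.43 | 22 + 7 = 29 |
| 26.8 (24.1 + 2.7) | 0.9 / 4.8 = 0.19 | 22 + 16 = 38 |
| 21.4 (24.1 − 2.7) | 0.9 / (−0.6), negative | method fails |

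A comparator with Dk/t of about 29 to 38 would thus match a fully successful Apioc lens by diffusion alone. At 0.20 mm that is Dk 58 to 76; at 0.10 mm it is Dk 29 to 38.

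**4. Whether the matched contrast must occur.** Three of the four lens types can be chosen in four ways: {i, ii, iii}, {i, ii, iv}, {i, iii, iv} and {ii, iii, iv}. One omits the standard lens. Only two contain both Apioc with lenticular (i) and the standard lens (iii). Under the shorter list in Clinical Study Methods, the standard lens need not be used at all.

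**5. Whether the contrast is analysed.** Data Analysis sets test conditions against open and closed eye. Even when lenses i and iii are both measured, no test of one against the other is planned.

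**The case against.** A reader might infer that the plan assumes the commercial lens has Dk/t 22 and then leaves it open. The documents do not support that. The Hypothesis attaches Dk/t 22 to the standard lens, and III.C lists the standard lens separately from the commercial one. Objective I can fairly be read as a whole-product comparison that makes no claim about mechanism. The Hypothesis also derives one Dk/t for both lenses from one material value and one thickness, which suggests that the standard lens was meant to share Apioc's material. Clinical Study Methods may be only a summary of the fuller list, and the limit of three lenses applies to a visit, while there may be up to three visits.

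Much of this stands. The plan does contain the beginnings of the right control. But the shared material is implied and not written, and Clinical Study Methods has the measurements repeated at two further visits, so later visits need not bring in a lens omitted at the first.

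It is also true that no planned test uses Apioc versus commercial to prove tear exchange: the experimental hypothesis is an absolute uptake threshold, and the t-tests are against open and closed eye. That limits the charge against the commercial contrast. It also confirms that no planned test compares Apioc with a matched lens.

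Two further inferences go too far. The documents do not say that commercial products will differ between subjects; they are silent. And they cannot support a figure for lost power or for false positive results: Number of Subjects gives 10 with no SD, effect size or alpha, and the EOP slope more than halves within the plan's own ± 2.7.

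**Conclusion.** The point holds as a gap in securing the matched comparison. The standard lens, which is the natural control for tear exchange, has no stated material, is missing from one of the two lens lists, can be left out, and is in no named contrast. The commercial lens is unspecified, so its difference from Apioc cannot separate permeability from tear exchange, and the documents fix no direction for the resulting bias.

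On size, a comparator Dk/t of about 29 to 38, against the assumed 22, offsets the whole hypothesised gain. This rests on EOP being linear in Dk/t, on pairing 9.9% EOP with the transmissibility benchmark (which the text implies but does not state), and on uptake following EOP. At the lower limit of the benchmark the calculation gives no answer, so the range is illustrative. The conclusion does not depend on it: the same material at half the thickness already doubles Dk/t.

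**What to change.** 1. In Clinical Study Methods and in III.C, require lens iii to be made in the Apioc material (Definitive 74), and list it in both places so that the two lists agree. Record its center thickness and Dk/t beside Apioc's, because the Hypothesis works from center thickness and III.C.iii from mean thickness.
2. Make Apioc with lenticular and lens iii two of the lenses measured in every subject.
3. In Data Analysis, prespecify the paired contrast of Apioc with lenticular versus lens iii as the test of tear exchange.
4. Use the same commercial product or products in all subjects. Report Apioc versus commercial as a whole-product comparison (material plus design), with each lens's Dk/t beside the estimate, and do not use it as evidence of tear exchange.

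This is a change of wording that adds no subjects, visits or measurements beyond the present maximum. The cost is that at most one lens slot per visit remains for Apioc without lenticular or a commercial lens, and that the commercial comparison supports a narrower claim.

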Corneal Oxygen Uptake with Apioc Contact Lenses

Protocol Len-003

Lentechs, LLC

Columbus, OH

Revision	Originator	Description of Changes	Date
0.0	[name], [name]	New Protocol	12/22/2018

Confidential

Background and Introduction	1
Tear Flow Under Hydrogel Contact Lenses	2
Study Objective	2
Hypothesis.....	2
Study Lenses.....	3
Subject Qualification	3
Number of Subjects.....	3
Inclusion Criteria	3
Exclusion Criteria.....	4
Study Design and Procedures	4
Study Design.....	4
Clinical Study Methods.....	4
Data Analysis	6
Safety and Adverse Events	6
Adverse Event (AE) Definitions.....	6
Causality Assessment	6
Severity Assessment.....	7
Adverse Event Follow-up.....	8
Adverse Event Reporting Timeline	9
Protocol Deviations	9
Appendix	10
Comfort Assessment	10
Brien Holden Vision Institute Grading Scales	11
Adverse Event Classification (AEC) Form.....	12
Adverse Event Follow-up Form	13
Adverse Event Outcome Form	13
References	14

Background and Introduction

The human cornea is an avascular tissue that receives its oxygen through the tear film. It is well accepted that contact lens wear interrupts this oxygen diffusion and results in physiologic changes (Smelser GK, 1955). Contact lens and oxygen metrics to prevent these physiologic changes due to contact lens wear like corneal swelling, limbal injection, and neovascularization have been calculated (Brennan NA, 1987; Papas, 1998; Yeung KK, 2018). The Apioch lens design differs from commercially available lenses primarily because it has greater on-eye movement. It is proposed that this greater movement allows for greater tear flow and thus greater oxygen diffusion to the cornea.

Human corneal oxygen uptake rate is measured by gently placing a polarographic oxygen sensor against the central cornea while the subject is seated in a chair and fixating a target straight in front of the subject on the wall. A Dual Channel oxygen meter with automated respirometry software amplifies the current output of the sensor and displays the oxygen tension in torr. The sensor has a flat, non-recessed 25 μm diameter silver anode covered by a nominal 12.5- μm polyethylene membrane. To maintain proper sensor function, as well as sanitary conditions, the membrane covering the sensor tip which contacts the cornea is changed between subjects.

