Calibration of the sensor allows for accurate measurements. The output of the sensor is zeroed by immersing the sensor into a 0.9 percent saline bath which has been bubbled with nitrogen from a compressed nitrogen gas cylinder for at least 60 minutes. Though dissolving sodium sulfite would create a more stable zero oxygen solution, this method is not safe for measurements being done on the human cornea *in vivo*. Nitrogen purging is considered the most effective method to remove dissolved oxygen for the stated purpose (Butler IB, 1994). The gain of the sensor's output is adjusted after immersion in a second bath of 0.9 percent saline bubbled with room air to establish an oxygen tension of approximately 154.3 torr (or, 20.9% of the average barometric pressure less the partial pressure of humidity). The temperature of both baths is controlled at 35.9°C, the average human corneal temperature (Purslow C, 2005).

Corneal oxygen uptake rates are derived by rapid transfer of the sensor from the 154.3-torr bath to gentle contact with mild consistent pressure against the central cornea. This transfer takes less than 2 sec. There is an initial upward burst of the sensor output to approximately 160 torr, after which the partial pressure of oxygen falls monotonically as the cornea depletes oxygen from the reservoir of the sensor (i.e., oxygen dissolved in the polyethylene jacket). Contact with the normal open-eye cornea is discontinued within approximately 28-40 seconds—when the cornea has depleted the oxygen reservoir below 40 torr. The corneal oxygen uptake rate is defined in mmHg/sec as the average depletion rate over the 100-mmHg range from 140 to 40 mmHg. It is important to note this difference in units (torr vs. mmHg) is negligible as one torr is equivalent to 0.999998575337 mmHg. The resting oxygen uptake rate of the normal open-eye human cornea measured in this manner will therefore vary from 3.5 to 4.5 mmHg/sec.

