Event is bothersome, possible requiring additional therapy, and may interfere with the subject's daily activities. Those events that are usually symptomatic and warrant discontinuation (temporary or permanent) of the test lens (excluding Serious Adverse Events).

Diagnoses and conditions that are considered Moderate Adverse Events include the following:

- Contact Lens Induced Peripheral Ulcer (CLPU)
- Significant Infiltrative Events (SIE)
- Superior Epithelial Arcuate Lesions (SEALs)
- Any Temporary Loss of 2 Lines of BSCVA
- Other grade 3 or higher corneal findings, such as abrasions or edema
- Any corneal event which necessitates temporary lens discontinuation for \geq 2 weeks
- Non-contact-lens-related-corneal-events – ex: EKC (Epidemic Keratoconjunctivitis)

- Asymptomatic Corneal Scar

Severe

Event is intolerable, necessitates additional therapy or alteration of therapy and interferes with the subject's daily activities. A serious AE is any untoward medical occurrence that:

- Results in death
- Is life threatening
- Requires in-patient hospitalization or prolongation of existing hospitalization
- Results in persistent or significant disability/incapacity
- Has potential to cause permanent impairment of a body function
- Has potential to cause damage to a body structure and may necessitate medical or surgical intervention

Diagnoses and conditions that are considered Serious Adverse Events include:

- Microbial Keratitis (MK)
- Iritis
- Permanent decrease in best spectacle corrected visual acuity equivalent to 2 acuity lines or greater
- Central Corneal Opacity
- Central Corneal Neovascularization
- Uveitis
- Endophthalmitis
- Hypopyon
- Hyphemia
- Penetration of Bowman's Membrane
- Persistent Epithelial Defect
- Limbal cell damage leading to conjunctivalization

Upon finding an adverse event, the Principal Investigator will document the condition on the follow-up visit examination form using photos or drawings (where appropriate) that detail size, location, and depth. He/she will also complete the Adverse Event Classification (AEC) Discovery Form.

Adverse Event Follow-up

It is the Investigator's responsibility to maintain documentation of each reported adverse event. All adverse events will be followed in accordance with standard of care. Such documentation will include the following:

- Diagnosis
- A description of the adverse event or ocular complication
- Detailed drawings or photographs, when appropriate
- Time of onset
- Duration of event

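### The irritation check before and between probe contacts names only the conjunctiva, although the probe touches the central cornea, and corneal findings have no named scale or graded baseline

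*Combined protocol and SAP*

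**What the plan says.** **Where the probe goes.** Background and Introduction describes "gently placing a polarographic oxygen sensor against the central cornea" and, for each reading, "gentle contact with mild consistent pressure against the central cornea". On duration it says "Contact with the normal open-eye cornea is discontinued within approximately 28-40 seconds".

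**How often.** Clinical Study Methods states "There will be up to five scenarios that will be examined at each visit". It adds that the measurements are repeated at two further visits, and Study Design allows up to three visits. One eye per subject is measured. Step IV.B of Oxygen Consumption of the Cornea Measurement has poor-quality measurements repeated and gives no maximum.

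**What is checked around each contact.** Clinical Study Methods says "The conjunctiva of the subject will be examined prior to probe applications and between probe applications to assess ocular irritation induced by the probe". It then ends measurements for the day on a two-grade increase on the appendix scales, without saying which scale. Step V.A begins "Visually assess conjunctival redness" and ties the two-grade increase to bulbar or limbal redness. Step V.B lets the subject decline another measurement.

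**What is checked before and after the measurements.** The Baseline and the Concluding Visual and Ocular Assessments each include visual acuity and an anterior segment slit lamp examination. The recorded item is "Ocular abnormalities noted".

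**How corneal findings are classified.** Severity Assessment lists as moderate "Other grade 3 or higher corneal findings, such as abrasions or edema", with no scale named. The appendix reproduces grading scales that include a corneal staining panel, but no procedure step calls for that panel.

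**The concern.** The interim check has a stated purpose, to detect irritation caused by the probe. As written, it is directed at tissue that the probe does not touch. An examiner following the text would look for redness and could move to the next contact without looking at the contacted cornea.

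Two things are at stake:

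- **Safety.** An epithelial disturbance from one contact might be noticed only at the concluding examination, after further contacts on the same spot.
- **Interpretation.** Uptake is measured on that same tissue. Without a record of corneal state between contacts, nobody could tell which readings followed a disturbance.

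Separately, the protocol uses a corneal grade to classify events but never asks for one. Its adverse event definition also counts a condition that was already present and then worsened. An ungraded note at baseline is a weak basis for judging worsening.

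**Working it through.** **Planned contacts per visit.** Step V.C counts the open-eye condition (1), the closed-eye condition (1) and up to three lenses (3): 1 + 1 + 3 = 5. This reproduces the stated maximum of five scenarios.

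**Planned contacts per subject.** 5 per visit x 3 visits = 15, all on one eye. For 10 subjects, 15 x 10 = 150. The protocol gives no per-subject total of its own.

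**Repeats.** The number of repeats is unlimited and no repeat rate is given. If a share r of measurements is repeated once (an assumption), the mean is 15 x (1 + r):

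| Assumed r | Mean contacts per subject |
|---|---|
| 0 | 15 |
| 10% | 16.5 |
| 20% | 18 |
| 50% | 22.5 |

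So 15 is the planned maximum, not an upper limit.

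**Contacts between two slit lamp examinations.** The protocol does not say whether the baseline and concluding assessments are done at every visit or once per study.

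| Reading | Slit lamp examinations | Planned contacts between baseline and concluding examination |
|---|---|---|
| Every visit | 2 x 3 = 6 | up to 5 |
| Once per study | 2 | up to 15 |

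**Readings exposed within a visit.** If a disturbance arose at the first contact, 5 - 1 = 4 readings that day would follow it. This counts positions only. It is not an estimate of bias, because the documents give neither a rate of probe-induced disturbance nor its effect in mmHg/sec.

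**The sections side by side.**

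| Point in the study | Tissue named | Graded? |
|---|---|---|
| Baseline slit lamp | Anterior segment, which includes the cornea | No |
| Before and between contacts | Conjunctiva | Bulbar or limbal redness (step V.A) |
| Concluding slit lamp | Anterior segment, which includes the cornea | No |
| Moderate event criterion | Cornea | Grade 3 or higher, scale not named |

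The one row that uses a corneal grade has no row above it that produces one.

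**The case against.** A reader might infer that corneal damage would go unseen altogether. The documents do not support that. Slit lamp examination and visual acuity come before and after the measurements, and clear, healthy corneas are an entry criterion that is re-checked at baseline. Subjects are eyecare clinicians or trainees, and any of them can end the visit by declining another measurement. What remains is the interval between contacts: willingness to continue is a real safeguard, but it does not record the state of the cornea.

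A reader might also infer that the grade 3 criterion cannot be applied. That is too strong. It is an absolute threshold, so an examiner who sees a finding can grade it without a baseline grade. The appendix offers a corneal staining panel. Corneal events are also sorted by how long lens wear is discontinued, and events are documented with photos or drawings where appropriate. What remains is that no scale is named, the legible appendix text shows none for edema (its figures are not available here), and no graded baseline exists for judging worsening.

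A third tempting inference is that the uptake comparison is biased. Scenario order is randomised, so carry-over would tend to add noise rather than favour one lens, and its existence is not shown.

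Two further points stand in part. Measurements follow a procedure manual that was not supplied, so extra corneal checks there cannot be excluded; the protocol cites that manual for equipment setup and data collection, not for the step V checks or the eye examinations. It is also fair that nothing in the documents shows how sensitive an undyed look would be.

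**Conclusion.** The point holds in a limited form. For up to 15 planned contacts per subject, and more with repeats, the check meant to detect probe-induced irritation names the conjunctiva while the contact is on the central cornea. A corneal disturbance could be missed between contacts within a visit and precede up to 4 of 5 readings that day. The grade 3 corneal criterion lacks a named scale and a graded baseline, but it can still be used.

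This rests on three assumptions: all five scenarios are run at all three visits; the slit lamp examinations are done at each visit (if they are done once per study, the interval covers up to 15 contacts); and the procedure manual adds no corneal check. The consequence for uptake cannot be quantified from the documents. This is a low-cost improvement to safety monitoring and record-keeping, not a flaw that invalidates the comparison.

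**What to change.** 1. Reconcile Clinical Study Methods and step V.A with Background and Introduction and with Severity Assessment, so that the existing check before and between contacts also covers the contacted central cornea. An undyed look, recorded as finding yes/no, fits within the existing rest of at least ten minutes.
2. Record corneal findings on a named scale at the baseline and concluding slit lamp examinations, and name that scale in the moderate event criterion. State whether these examinations are done at every visit.
3. In the same edit, reconcile the two wordings of the two-grade rule, which differ on which scales count.
4. Flag readings taken after a recorded corneal finding. A descriptive sensitivity analysis without them is optional; with 10 subjects it would leave fewer complete pairs for the paired t-tests.

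What is done clinically on such a finding is for the investigator and the reconciled text.

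The cost is a short added examination step and one form line per contact, plus a grade at two examinations already scheduled. The slit lamp is specified now only at baseline and conclusion, so using it between contacts would add some handling time; the documents give no figure for this.
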